6.2 Sample Size Determination

Anticipating all cohorts are to be assessed in the study, approximately 90 participants will be randomized in a 5:1 ratio to either TBA-7371 or control group, totaling N = 15 participants for each TBA-7371 treatment and control groups (receiving treatment with HRZE).

Bactericidal effect

Based on Diacon et al. (Diacon, 2013) standard deviations associated with BAcfu(0-14) were relatively consistent across 5 treatment groups, ranging from 0.05 to 0.08. If we assume conservatively that the true standard deviation of the BAcfu(0-14) measures for the TBA-7371 treatment groups is equal to 0.1, then with N = 15 per group we have 80% (90%) power to detect a true group mean BAcfu(0-14) reduction of 0.067 (0.079), using a 1-sided alpha = 5%. For reference, the observed BAcfu(0-14) reduction in Diacon et al, 2013 were 0.040, 0.056, 0.077, 0.104, and 0.122 for Bedaquiline 100 mg, 200 mg, 300 mg, 400 mg and standard HRZE, respectively.

Safety

With N = 15 per group, we have approximately 80% (90%) probability to observe at least one AE if the true AE rate is 10% (15%). We have only 54% probability to observe at least one AE if the true AE rate is 5%. Across the five TBA-7371 treatment groups (N=75), we have 90% probability to observe at least one AE if the true AE rate is 3.0%.

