regression model for individual participants in each treatment group in order to ensure the Akaike information criteria (AIC) values for the linear and bilinear models are based on the same form of the likelihood function. Suggested starting values for the parameters are $(\alpha, \beta_1) = (6, 0)$ however a grid search approach can be followed to obtain sensible starting values.

If the linear regression model is selected, the average change in $\log_{10}\text{CFU}/\text{mL}$ count per day over 14 days will be estimated by the constant linear regression slope estimate, $\hat{\beta}_{1i}$, i.e.

$$BA_{CFU}(0 - 14)_i = \hat{\beta}_{1i}.$$

Therefore, for each participant, slopes will be estimated using both bilinear and simple linear regression models, and the better fit model based on lower AIC will be selected for that participant and used to estimate $BA_{CFU}(0-14)$. The $\log_{10}\text{CFU}/\text{mL}$ screening measurement used in the model will be the average of the two individual screening measurements. $BA_{CFU}(0-14)$ will be calculated for each participant within a treatment group individually, and then used as the response variable in an ANCOVA model, with a fixed effect for treatment group and screening $\log_{10}\text{CFU}/\text{mL}$ count as a covariate. Treatment group means from the ANCOVA model will be used to quantify the evidence that each of the treatment group mean $BA_{CFU}(0-14)$ is less than 0 (i.e., that the treatment group mean has a negative slope on average). The mITT population will be used for the primary efficacy analysis with analyses using the per-protocol population performed to assess the robustness of results. The SAS PROC MIXED procedure will be used to fit an ANCOVA model.

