  class <treatment group>(ref=HRZE);
  model <Avg. Slope(0-14)> = <treatment group> + <screening
logCFU> /
* LSmeans used to obtain 90 CIs;
  lsmeans <treatment group> / cl alpha=0.1;
* 6 LSMestimate statements used to obtain 1-sided p-values -
NOTE: HRZE will refer to #6 below if used as reference, the #1-5 will
be as indicated in model;;
  lsmestimate <trt> 'trt #1' 1 0 0 0 0 0 / lower alpha = 0.05;
  lsmestimate <trt> 'trt #2' 0 1 0 0 0 0 / lower alpha = 0.05;
  lsmestimate <trt> 'trt #3' 0 0 1 0 0 0 / lower alpha = 0.05;
  lsmestimate <trt> 'trt #4' 0 0 0 1 0 0 / lower alpha = 0.05;
  lsmestimate <trt> 'trt #5' 0 0 0 0 1 0 / lower alpha = 0.05;
  lsmestimate <trt> 'trt #6' 0 0 0 0 0 1 / lower alpha = 0.05;
run;
```

SAS code for random intercepts and slopes model (day = relative to baseline study day, trt = treatment group with HRZE as reference):

```
proc mixed data=<dataset>;
  class <treatment group>(ref=HRZE) <subject>;
  model logCFU = <day> + <trt> + <day*trt> + <screening logCFU>;
  random int day / subject=<subject> type=un;
* The first 6 estimate statements used to obtain correct 1-sided p-
values - NOTE: HRZE will refer to #6 below if used as reference, the
#1-5 will be as indicated in model;
  estimate "Avg slope Tr 1" day 1 trt*day 1 0 0 0 0 0 / cl lower
alpha =0.05;
  estimate "Avg slope Tr 2" day 1 trt*day 0 1 0 0 0 0 / cl lower alpha
=0.05;
  estimate "Avg slope Tr 3" day 1 trt*day 0 0 1 0 0 0 / cl lower alpha
=0.05;
  estimate "Avg slope Tr 4" day 1 trt*day 0 0 0 1 0 0 / cl lower alpha
=0.05;
  estimate "Avg slope Tr 5" day 1 trt*day 0 0 0 0 1 0 / cl lower alpha
=0.05;
  estimate "Avg slope Tr 6" day 1 trt*day 0 0 0 0 0 1 / cl lower alpha
=0.05;
* The next 6 estimate statements used to obtain correct 90% CIs;
  estimate "Avg slope Tr 1" day 1 trt*day 1 0 0 0 0 0 / cl alpha =0.1;
  estimate "Avg slope Tr 2" day 1 trt*day 0 1 0 0 0 0 / cl alpha =0.1;
  estimate "Avg slope Tr 3" day 1 trt*day 0 0 1 0 0 0 / cl alpha =0.1;
  estimate "Avg slope Tr 4" day 1 trt*day 0 0 0 1 0 0 / cl alpha =0.1;
  estimate "Avg slope Tr 5" day 1 trt*day 0 0 0 0 1 0 / cl alpha =0.1;
  estimate "Avg slope Tr 6" day 1 trt*day 0 0 0 0 0 1 / cl alpha =0.1;
run;
```

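### Each regimen is tested against zero with one residual variance pooled over all six groups, so its nominal 5% depends on an equal-variance assumption that the plan neither states nor checks; a group-specific variance is a cheap safeguard

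*SAP*

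**What the plan says.** SAP 11.1.1 estimates a slope for each participant. The slope is then "used as the response variable in an ANCOVA model, with a fixed effect for treatment group and screening" log CFU as the covariate. The hypothesis for each regimen is that its adjusted mean is below zero; it is not a comparison with HRZE.

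Appendix 4 carries this out with one PROC MIXED call in which HRZE is the sixth level of the treatment factor. Each mean has its own one-sided statement, for example "lsmestimate <trt> 'trt #1' 1 0 0 0 0 0 / lower alpha = 0.05". The printed code has no REPEATED / GROUP= statement and no robust-variance option. The 90% confidence intervals come from the same fit.

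SAP 6.2 plans on 15 participants per group. It reports SDs from the cited bedaquiline study as "relatively consistent across 5 treatment groups, ranging from 0.05 to 0.08" and then assumes that the SD for the TBA-7371 "treatment groups is equal to 0.1". On that basis it claims "80% (90%) power to detect a true group mean BAcfu(0-14) reduction of 0.067 (0.079") at a one-sided 5% level.

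Neither CFU sensitivity analysis lets the variance differ by group. SAP 11.1.3.1 refits the same ANCOVA to average change from baseline, and SAP 11.1.3.2 is a random-slope model with variances common to all groups.

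**The concern.** In a contrast between two equal-sized groups, unequal variances largely average out. In a test of one group against zero they do not. The standard error should reflect that group's own spread, and here it reflects the average spread of six groups. A group more variable than average is tested too liberally, and a less variable one too strictly.

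The p-values affected are the ones that decide the trial. They feed the 0.05/0.025 Hochberg rule within each testing group, they determine whether the lower-dose groups are formally tested, and one significant regimen with acceptable safety makes the study a success. An over-strict test matters too: a high-dose regimen with uniform response could fail and block testing of the lower doses.

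**Working it through.** **Inputs.** Six groups of 15 (SAP 6.2). One-sided 0.05, with 0.025 as the smaller Hochberg threshold (SAP 11.1.1). Planning SD 0.1, and reference-study SDs of 0.05 to 0.08 (SAP 6.2). Pooled error df = 90 − 6 − 1 = 83.

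**The plan's power figure.** For a one-group t-test with n = 15 and SD 0.1, using the noncentral t distribution:

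| Variance used | Power at 0.067 | Power at 0.079 | Detectable at 80% / 90% |
|---|---|---|---|
| Own group, 14 df | 79.4% | 89.7% | 0.0675 / 0.0795 |
| Pooled, 83 df | 82.4% | 91.8% | 0.0647 / 0.0762 |

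The stated 80% and 90% match the own-variance test better than the pooled test in Appendix 4.

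**Type I error of the pooled test.** With s_g the true SD of the tested group and s_p² the mean of the six group variances, the size is approximately 1 − Φ(t × s_p / s_g), where t = 1.663 (one-sided 5%, 83 df). The formula treats s_p as known, so it gives 4.8% where the exact value is 5.0%. A simulation of the six-group ANCOVA with a covariate (60,000 trials per setting) is shown beside it.

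- *All SDs 0.1 (the plan's assumption).* Exact size 5.0%; simulation 4.9%.
- *TBA-7371 groups 0.1, HRZE 0.05.* s_p² = (5 × 0.01 + 0.0025)/6 = 0.00875, s_p = 0.0935, 1.663 × 0.935 = 1.556. Formula 6.0%; simulation 6.2%.
- *TBA-7371 groups 0.1, HRZE 0.08.* s_p² = (0.05 + 0.0064)/6 = 0.0094, s_p = 0.0970. Formula 5.3%; simulation about 5.5%.
- *SDs evenly spread: 0.050, 0.056, 0.062, 0.068, 0.074, 0.080.* s_p² = 0.02598/6 = 0.00433, s_p = 0.0658.
  - Most variable group: 1.663 × 0.0658/0.08 = 1.368. Formula 8.6%; simulation 8.8%.
  - Least variable group: 1.663 × 0.0658/0.05 = 2.189. Formula 1.4%; simulation 1.7%.
- *Tested group 0.08, other five 0.05.* s_p² = (0.0064 + 5 × 0.0025)/6 = 0.00315, s_p = 0.0561, 1.663 × 0.0561/0.08 = 1.167. Formula and simulation 12.2%. At the 0.025 threshold, 8.1% by formula and 8.3% by simulation.
- *Tested group 0.05, other five 0.08.* s_p² = (0.0025 + 5 × 0.0064)/6 = 0.00575, s_p = 0.0758, 1.663 × 0.0758/0.05 = 2.52. Formula 0.6%; simulation 0.7%.

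**Error of the Hochberg rule in Group 1, both means at zero (simulation).** With equal SDs it is 4.9%. With the even spread it is 9.2% if the pair are the two most variable groups and 1.7% if they are the two least variable. If both have SD 0.08 and the other four 0.05 it is 12.4%; in the reverse case it is 0.6%.

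**With the group's own variance.** Approximated by the own-group standard error and 14 df, the size of the single test is 5.0% to 5.3% across the six-group settings with n = 15, and the Group 1 Hochberg error is 5.1% to 5.4%. The Kenward-Roger fit itself was not run.

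**The case against.** The strongest reply is that the plan does not expect unequal variances. It adopts one SD of 0.1 for every TBA-7371 group, and under that assumption the test is correct, or close to it if only HRZE differs. This stands, and the size under the plan's own assumption is 5.0%.

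A reader might infer from "standard deviations associated with BAcfu(0-14) were relatively consistent across 5 treatment groups, ranging from 0.05 to 0.08" that the plan itself concedes a variance ratio of (0.08/0.05)² = 2.56, so that the test really runs at 12%. The documents do not support that. The figures are observed SDs from a study of bedaquiline and HRZE. If those groups had about 15 patients each (an assumption; the documents do not give the size), five groups with one common true SD would show a largest-to-smallest ratio of 1.6 or more about 42% of the time. The 12% and 0.6-0.7% figures also come from two mutually exclusive arrangements, each with one group at one end of the range and the other five at the opposite end. Across the six groups of an even spread the errors roughly balance (4.8% on average), so error is redistributed and not inflated throughout.

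A common-variance ANCOVA is also a standard prespecified model, and separate variances from about 15 participants each are less precise. That is a fair trade-off to argue. But the plan does not argue it, and its stated power already accepts the lower df.

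Finally, the MODEL statement in the available text ends at a slash with no options shown, so a df option may have been lost. That would not supply the absent REPEATED statement.

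**Conclusion.** The point holds as a cheap improvement, not as a demonstrated error in the primary test. Each regimen's test keeps its nominal 5% only if all six groups, HRZE included, share a variance. The plan neither states this as an analysis assumption nor checks it, and no sensitivity analysis relaxes it.

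The size depends on the true SDs. It is 5.0% under the planning assumption and about 6% if HRZE alone has SD 0.05. It is about 8-9% for the most variable group and 1.7% for the least if true SDs were spread evenly over 0.05 to 0.08. About 12% and 0.6-0.7% are limits within that range, not expected values. All of these assume 15 per group and normal slopes. With 13 per group the two limits barely move (12.3% and 0.7%).

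**What to change.** In the primary ANCOVA of Appendix 4, add `repeated / group=<treatment group>;` and name a small-sample df method (Kenward-Roger or Satterthwaite). State in SAP 11.1.1 that each mean is tested with its own group's residual variance, and report the pooled-variance model as a sensitivity analysis. At minimum, keep the present model as primary and prespecify the group-specific-variance test as a sensitivity analysis.

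The cost is two code options and a sentence or two in the SAP. Data collection and sample size do not change. Each test has about 14 instead of 83 error df, so the one-sided critical value rises from about 1.66 to 1.76. Because the stated 0.067 and 0.079 already reproduce with 14 df, essentially none of the stated power is given up.

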Appendix 5 Document History

DOCUMENT HISTORY	
Document	Date
Original SAP	22 Nov 2019
Amendment 1	23 Aug 2021
Amendment 2	27 June 2022

Changes in Amendment 1:

Modifications were made to the following sections of the SAP:

Section 4.0 Introduction

- Revise text with respect to the protocol amendment

Section 5.2 Objectives and Endpoint

- Revise text with respect to the protocol amendment

Section 6 Study Design Considerations

- Revise text with respect to the protocol amendment

Section 7 Study Population

- Remove completer population

Section 9 Overall Statistical Considerations

- Define baseline values of vital signs

Section 10 Statistical Analysis Methods

- Add drug susceptibilities and MIC of TBA-7371 to summary of baseline characteristics

Section 11

- Add description for computing CFU/mL

Section 12 Safety Analyses

- Clarify determination of AEs of special interest per Investigator discretion
- Add line plots of mean of intraday and daily heart rate, SBP, and DBP in supine and standing position
- Add line plots of mean of orthostatic change in intraday and daily heart rate, SBP, and DBP
- Add boxplots of intraday and daily values of QTcF
- Revise analyses for eye symptoms, visual acuity, and color vision test

- Add summary of COVID-19/SARS-CoV-2 test
- Add summary of drug susceptibilities and MIC of TBA-7371

Section 16 References

- Update references

Changes in Amendment 2:

Modifications were made to the following sections of the SAP:

Section 2 Signature Page

- Author of SAP changed from [REDACTED] to [REDACTED]
- Approval changed from [REDACTED] to [REDACTED]

Section 7.1 Population for Analyses

- Randomized population definition added.
- Clarity added for the timing of PK samples to the PK population definition.

Section 11.1.1 Primary Analysis

- Clarity added for starting values for the bilinear regression model
- Clarity added regarding equations, refined definition of BACfu(0-14) for bilinear model
- Clarity added to use of PROC NLMIXED for both linear and bilinear models

Section 11.1.2 Secondary Analysis

- Clarity added to bilinear models used for secondary analysis.

Section 11.1.3 Sensitivity Analysis

- Updated the use of Bayesian model to ANCOVA using averaged change from baseline, as well as a mixed model

Section 11.3 Subgroups

- Added HIV status at Baseline as a subgroup.

Section 13.2 Pharmacokinetic analyses

- Clarity added regarding models and statistics used for reporting

